8.1.3 Subject Exclusion Criteria

The subject must be excluded from participating in the trial if the subject:

1. Is currently participating and receiving study therapy or has participated in a study of an investigational agent and received study therapy or used an investigational device within 4 weeks of the first dose of treatment.
2. Has squamous cell or undifferentiated gastric cancer.
3. Has a diagnosis of immunodeficiency or is receiving systemic steroid therapy or any other form of immunosuppressive therapy within 7 days prior to the first dose of trial treatment.
4. Has a known history of active TB (Bacillus Tuberculosis)
5. Hypersensitivity to pembrolizumab or any of its excipients.
6. Has had a prior anti-cancer monoclonal antibody (mAb) within 4 weeks prior to study Day 1 or who has not recovered (i.e., \leq Grade 1 or at baseline) from adverse events due to agents administered more than 4 weeks earlier.
7. Has had prior chemotherapy, targeted small molecule therapy, or radiation therapy within 2 weeks prior to study Day 1 or who has not recovered (i.e., \leq Grade 1 or at baseline) from adverse events due to a previously administered agent.
 - Note: Subjects with \leq Grade 2 neuropathy are an exception to this criterion and may qualify for the study.
 - Note: If subject received major surgery, they must have recovered adequately from the toxicity and/or complications from the intervention prior to starting therapy.
8. Has a known additional malignancy that is progressing or requires active treatment. Exceptions include basal cell carcinoma of the skin or squamous cell carcinoma of the skin that has undergone potentially curative therapy or in situ cervical cancer.
9. Has known active central nervous system (CNS) metastases and/or carcinomatous meningitis. Subjects with previously treated brain metastases may participate provided they are stable (without evidence of progression by imaging for at least four weeks prior to the first dose of trial treatment and any neurologic symptoms have returned to baseline), have no evidence of new or enlarging brain metastases, and are

not using steroids for at least 7 days prior to trial treatment. This exception does not include carcinomatous meningitis which is excluded regardless of clinical stability.

10. Has active autoimmune disease that has required systemic treatment in the past 2 years (i.e. with use of disease modifying agents, corticosteroids or immunosuppressive drugs). Replacement therapy (e.g., thyroxine, insulin, or physiologic corticosteroid replacement therapy for adrenal or pituitary insufficiency, etc.) is not considered a form of systemic treatment.
11. Has known history of, or any evidence of active, non-infectious pneumonitis.
12. Has an active infection requiring systemic therapy.
13. Has a history or current evidence of any condition, therapy, or laboratory abnormality that might confound the results of the trial, interfere with the subject's participation for the full duration of the trial, or is not in the best interest of the subject to participate, in the opinion of the treating investigator.
14. Has known psychiatric or substance abuse disorders that would interfere with cooperation with the requirements of the trial.
15. Is pregnant or breastfeeding, or expecting to conceive or father children within the projected duration of the trial, starting with the pre-screening or screening visit through 120 days after the last dose of trial treatment.
16. Has received prior therapy with an anti-PD-1, anti-PD-L1, or anti-PD-L2 agent.
17. Has a known history of Human Immunodeficiency Virus (HIV) (HIV 1/2 antibodies).
18. Has known active Hepatitis B (e.g., HBsAg reactive) or Hepatitis C (e.g., HCV RNA [qualitative] is detected).
19. Has received a live vaccine within 30 days of planned start of study therapy.

Note: Seasonal influenza vaccines for injection are generally inactivated flu vaccines and are allowed; however intranasal influenza vaccines (e.g., Flu-Mist®) are live attenuated vaccines, and are not allowed.

20. Is or has an immediate family member (e.g., spouse, parent/legal guardian, sibling or child) who is investigational site or staff directly involved with this trial, unless prospective IRB approval (by chair or designee) is given allowing exception to this criterion for a specific subject.

8.2 Trial Treatments

The treatment to be used in this trial is outlined below in Table 2

Table 2 Trial Treatment

Drug	Dose/Potency	Dose Frequency	Route of Administration	Regimen/Treatment Period	Use
Pembrolizumab	200 mg X mg/kg	Q3W	IV infusion	Day 1 of each 3 week cycle	Experimental

8.2.1 Dose Selection/Modification

8.2.1.1 Dose Selection

The rationale for selection of doses to be used in this trial is provided in Background and Rationale.

8.2.1.2 Dose Modification

Adverse events (both non-serious and serious) associated with pembrolizumab exposure may represent an immunologic etiology. These adverse events may occur shortly after the first dose or several months after the last dose of treatment. Pembrolizumab must be withheld for drug-related toxicities and severe or life-threatening AEs as per Table 3 below. Events of Clinical Interest Guidance Document for supportive care guidelines, including use of corticosteroids.

Table 3

Dose Modification Guidelines for Drug-Related Adverse Events

Toxicity	Hold Treatment For Grade	Timing for Restarting Treatment	Discontinue Subject
Diarrhea/Colitis	2-3	Toxicity resolves to Grade 0-1.	Toxicity does not resolve within 12 weeks of last dose or inability to reduce corticosteroid to 10 mg or less of prednisone or equivalent per day within 12 weeks.
	4	Permanently discontinue	Permanently discontinue
AST, ALT, or Increased Bilirubin	2	Toxicity resolves to Grade 0-1	Toxicity does not resolve within 12 weeks of last dose.
	3-4	Permanently discontinue (see exception below) ¹	Permanently discontinue
Type 1 diabetes mellitus (if new onset) or Hyperglycemia	T1DM or 3-4	Hold pembrolizumab for new onset Type 1 diabetes mellitus or Grade 3-4 hyperglycemia associated with evidence of beta cell failure.	Resume pembrolizumab when patients are clinically and metabolically stable.
Hypophysitis	2-3	Toxicity resolves to Grade 0-1	Toxicity does not resolve within 12 weeks of last dose or inability to reduce corticosteroid to 10 mg or less of prednisone or equivalent per day within 12 weeks.
	4	Permanently discontinue	Permanently discontinue
Hyperthyroidism	3	Toxicity resolves to Grade 0-1	Toxicity does not resolve within 12 weeks of last dose or inability to reduce corticosteroid to 10 mg or less of prednisone or equivalent per day within 12 weeks.
	4	Permanently discontinue	Permanently discontinue

Toxicity	Hold Treatment For Grade	Timing for Restarting Treatment	Discontinue Subject
Hypothyroidism	2-4	Therapy with pembrolizumab can be continued while treatment for the thyroid disorder is instituted	Therapy with pembrolizumab can be continued while treatment for the thyroid disorder is instituted.
Infusion Reaction	3-4	Permanently discontinue	Permanently discontinue
Pneumonitis	2	Toxicity resolves to Grade 0-1	Toxicity does not resolve within 12 weeks of last dose or inability to reduce corticosteroid to 10 mg or less of prednisone or equivalent per day within 12 weeks.
	3-4	Permanently discontinue	Permanently discontinue
Renal Failure or Nephritis	2	Toxicity resolves to Grade 0-1	Toxicity does not resolve within 12 weeks of last dose or inability to reduce corticosteroid to 10 mg or less of prednisone or equivalent per day within 12 weeks.
	3-4	Permanently discontinue	Permanently discontinue
All Other Drug-Related Toxicity ²	3 or Severe	Toxicity resolves to Grade 0-1	Toxicity does not resolve within 12 weeks of last dose or inability to reduce corticosteroid to 10 mg or less of prednisone or equivalent per day within 12 weeks.
	4	Permanently discontinue	Permanently discontinue

Note: Permanently discontinue for any severe or Grade 3 drug-related AE that recurs or any life-threatening event.

¹ For patients with liver metastasis who begin treatment with Grade 2 AST or ALT, if AST or ALT increases by greater than or equal to 50% relative to baseline and lasts for at least 1 week then patients should be discontinued.

² Patients with intolerable or persistent Grade 2 drug-related AE may hold study medication at physician discretion. Permanently discontinue study drug for persistent Grade 2 adverse reactions for which treatment with study drug has been held, that do not recover to Grade 0-1 within 12 weeks of the last dose.

Dosing interruptions are permitted in the case of medical / surgical events or logistical reasons not related to study therapy (e.g., elective surgery, unrelated medical events, patient vacation, and/or holidays). Subjects should be placed back on study therapy within 3 weeks of the scheduled interruption. The reason for interruption should be documented in the patient's study record.

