8.3.2 Prohibited Concomitant Medications

Subjects are prohibited from receiving the following therapies during the Screening and Treatment Phase (including retreatment for post-complete response relapse) of this trial:

- Antineoplastic systemic chemotherapy or biological therapy
- Immunotherapy not specified in this protocol
- Chemotherapy not specified in this protocol
- Investigational agents other than pembrolizumab
- Radiation therapy
 - Note: Radiation therapy to a symptomatic solitary lesion or to the brain may be allowed at the investigator's discretion.
- Live vaccines within 30 days prior to the first dose of trial treatment and while participating in the trial. Examples of live vaccines include, but are not limited to, the following: measles, mumps, rubella, varicella/zoster, yellow fever, rabies, BCG, and typhoid vaccine.
- Systemic glucocorticoids for any purpose other than to modulate symptoms from an event of clinical interest of suspected immunologic etiology. The use of physiologic doses of corticosteroids may be approved after consultation with the Merk.

Subjects who, in the assessment by the investigator, require the use of any of the aforementioned treatments for clinical management should be removed from the trial. Subjects may receive other medications that the investigator deems to be medically necessary.

The Exclusion Criteria describes other medications which are prohibited in this trial.

There are no prohibited therapies during the Post-Treatment Follow-up Phase.

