8.4 Rescue Medications & Supportive Care

8.4.1 Supportive Care Guidelines

Subjects should receive appropriate supportive care measures as deemed necessary by the treating investigator. Suggested supportive care measures for the management of adverse events with potential immunologic etiology are outlined below and in greater detail in the ECI guidance document. Where appropriate, these guidelines include the use of oral or intravenous treatment with corticosteroids as well as additional anti-inflammatory agents if symptoms do not improve with administration of corticosteroids. Note that several courses of steroid tapering may be necessary as symptoms may worsen when the steroid dose is decreased. For each disorder, attempts should be made to rule out other causes such as metastatic disease or bacterial or viral infection, which might require additional supportive care. The treatment guidelines are intended to be applied when the investigator determines the events to be related to pembrolizumab.

Note: if after the evaluation the event is determined not to be related, the investigator is instructed to follow the ECI reporting guidance but does not need to follow the treatment guidance (as outlined in the ECI guidance document). Refer to Section 5.2.1 for dose modification.

It may be necessary to perform conditional procedures such as bronchoscopy, endoscopy, or skin photography as part of evaluation of the event. Suggested conditional procedures, as appropriate, can be found in the ECI guidance document.

- **Pneumonitis:**

- For **Grade 2 events**, treat with systemic corticosteroids. When symptoms improve to Grade 1 or less, steroid taper should be started and continued over no less than 4 weeks.
- For **Grade 3-4 events**, immediately treat with intravenous steroids. Administer additional anti-inflammatory measures, as needed.
- Add prophylactic antibiotics for opportunistic infections in the case of prolonged steroid administration.

- **Diarrhea/Colitis:**

Subjects should be carefully monitored for signs and symptoms of enterocolitis (such as diarrhea, abdominal pain, blood or mucus in stool, with or without fever) and of bowel perforation (such as peritoneal signs and ileus).

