 - Treat with an initial dose of IV corticosteroid followed by oral corticosteroids. When symptoms improve to Grade 1 or less, steroid taper should be started and continued over no less than 4 weeks. Replacement of appropriate hormones may be required as the steroid dose is tapered.
- **Hepatic:**
 - For **Grade 2** events, monitor liver function tests more frequently until returned to baseline values (consider weekly).
 - Treat with IV or oral corticosteroids
 - For **Grade 3-4** events, treat with intravenous corticosteroids for 24 to 48 hours.
 - When symptoms improve to Grade 1 or less, a steroid taper should be started and continued over no less than 4 weeks.
- **Renal Failure or Nephritis:**
 - For **Grade 2** events, treat with corticosteroids.
 - For **Grade 3-4** events, treat with systemic corticosteroids.
 - When symptoms improve to Grade 1 or less, steroid taper should be started and continued over no less than 4 weeks.
- **Management of Infusion Reactions:** Signs and symptoms usually develop during or shortly after drug infusion and generally resolve completely within 24 hours of completion of infusion.

Table 4 below shows treatment guidelines for subjects who experience an infusion reaction associated with administration of pembrolizumab (MK-3475).

Table 4 Infusion Reaction Treatment Guidelines

NCI CTCAE Grade	Treatment	Premedication at subsequent dosing
Grade 1 Mild reaction; infusion interruption	Increase monitoring of vital signs as medically indicated until the subject is deemed medically	None

NCI CTCAE Grade	Treatment	Premedication at subsequent dosing
not indicated; intervention not indicated	stable in the opinion of the investigator.	

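### Table 3 allows pembrolizumab to restart at Grade 0-1 with no limit on steroid dose, at the point where section 8.4.1 begins a steroid taper of at least four weeks

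*Combined protocol and SAP*

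**What the plan says.** **Restart (section 8.2.1.2, Table 3).** The restart column reads "Toxicity resolves to Grade 0-1", and nothing else, for seven rows: diarrhea/colitis, Grade 2 AST/ALT/bilirubin, hypophysitis, hyperthyroidism, pneumonitis, renal failure/nephritis, and the row for all other drug-related toxicity.

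**Discontinuation (same table).** Six of these rows also stop the subject for "inability to reduce corticosteroid to 10 mg or less of prednisone or equivalent per day within 12 weeks". The Grade 2 hepatic row does not; its only stop is failure of the toxicity to resolve within 12 weeks of the last dose.

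**Taper (section 8.4.1).** The pneumonitis guidance says "When symptoms improve to Grade 1 or less, steroid taper should be started and continued over no less than 4 weeks", and equivalent wording covers colitis, hypophysitis, Grade 3-4 hyperthyroidism and renal events. For Grade 2 hepatic events the section says "Treat with IV or oral corticosteroids", and its hepatic taper line reads "When symptoms improve to Grade 1 or less, a steroid taper should be started and continued over no less than 4 weeks". The section also warns that "several courses of steroid tapering may be necessary as symptoms may worsen when the steroid dose is decreased".

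**Concomitant steroids (section 8.3.2).** Systemic glucocorticoids are prohibited "for any purpose other than to modulate symptoms from an event of clinical interest of suspected immunologic etiology", so steroids given for an immune event are exempt.

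**The concern.** One clinical observation, improvement to Grade 1 or less, both opens the gate to re-dosing and marks the start of steroid withdrawal. At that moment the patient may still be on the full treatment dose of steroid. Grade 0-1 then shows that the event is controlled on steroid; it does not show that control will last at a low dose, and section 8.4.1 itself warns of worsening as the dose falls.

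What is at stake is patient safety and the chance of staying on treatment. Under Table 3 a Grade 3 hepatic, pneumonitis or renal event means permanent discontinuation, so a flare after an early restart could cost the patient the drug. No efficacy figure or sample-size calculation depends on this point.

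**Working it through.** **Step 1: compare the rows.** Inputs are Table 3 and the supportive-care bullets in section 8.4.1.

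| Table 3 row | Held grade | Steroids in 8.4.1 at that grade | Taper of 4 weeks or more from Grade 1 or less | Steroid limit at restart | 10 mg/day stop at 12 weeks |
|---|---|---|---|---|---|
| Diarrhea/colitis | 2-3 | If Grade 2 lasts over 3 days, or Grade 3 over 1 week | Yes | No | Yes |
| AST/ALT/bilirubin | 2 | Yes | Yes | No | **No** |
| Hypophysitis | 2-3 | Yes | Yes | No | Yes |
| Hyperthyroidism | 3 | Yes | Yes | No | Yes |
| Pneumonitis | 2 | Yes | Yes | No | Yes |
| Renal | 2 | Yes | Yes | No | Yes |
| All other | 3 or severe | Not addressed | No | No | Yes |

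Of seven rows, none has a steroid limit at restart, six have a taper rule, six have the 10 mg stop, and five have both.

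**Step 2: calendar overlap.** The dosing interval is 21 days, with a window of 3 days either side (section 8.2.2). The minimum taper is 4 × 7 = 28 days. Let u be the days from taper start to the next scheduled Day 1, u = 0 to 20, and assume dosing resumes there. Doses fall on days u and u + 21.

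- On schedule: the first dose is always before day 28; the second is if u + 21 < 28, so u < 7. Two doses for 7 of 21 offsets, one for 14 of 21.
- All doses 3 days late: u + 24 < 28, so u < 4. Two for 4 of 21, one for 17 of 21.
- All doses 3 days early (never before day 0): u + 18 < 28, so u < 10. Two for 10 of 21, one for 11 of 21.

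**Step 3: doses given above 10 mg/day.** These are the doses a restart limit would defer. They cannot be derived, because the documents state no starting dose or taper schedule. As an illustration only, assume a straight-line taper from D mg/day to zero over 28 days. Then 10 mg/day is reached on day 28 × (1 − 10/D).

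| Assumed D (mg/day) | Day 10 mg is reached | Offsets with no dose above 10 mg | One dose | Two doses |
|---|---|---|---|---|
| 10 or less | Start | 21 | 0 | 0 |
| 20 | 14.0 | 7 | 14 | 0 |
| 40 | 21.0 | 0 | 21 | 0 |
| 60 | 23.3 | 0 | 18 | 3 |
| 80 | 24.5 | 0 | 17 | 4 |

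The documents give no frequency for these events, so none of these counts converts to an expected number of patients.

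**The case against.** The strongest reply is that the threshold is already there. In five of the six taper rows, a patient who cannot get down to 10 mg/day within 12 weeks must stop. Read across the row, that looks like a deadline for clearing substantial steroid during the hold, and it would have little purpose once dosing had resumed. This stands as evidence of intent, but a deadline for giving up does not fix the dose at which restart is allowed, and the Grade 2 hepatic row has no such number.

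Second, both Table 3's introduction and section 8.4.1 refer to a separate ECI guidance document, which may set a restart condition. This stands: the gap can be asserted only for the supplied text.

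Third, section 8.3 carries medications barred by the exclusion criteria into the trial, and exclusion 3 bars systemic steroids. That exclusion concerns only the 7 days before the first dose, and the specific exemption in section 8.3.2 prevails for immune events.

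Fourth, other safeguards exist: ECI assessment and laboratory review before each dose, medication review each cycle, a new hold if the event returns to Grade 2 (in five of the six rows; hyperthyroidism acts only at Grade 3), and the table note "Permanently discontinue for any severe or Grade 3 drug-related AE that recurs or any life-threatening event". These give partial protection. None limits the steroid dose at restart.

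A reader might infer that the protocol tells investigators to re-dose during the taper, or that Table 3 and section 8.4.1 contradict each other. Neither follows. Restart is permitted, not required; the section 8.4.1 measures are described as suggested; and both rules can be followed by waiting. Nor does every held patient receive steroids: a Grade 2 colitis lasting 3 days or less need not.

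**Conclusion.** The point holds as a cheap safety improvement, not as the correction of an error. On the supplied text, restart is allowed at any steroid dose once the toxicity is Grade 0-1, and for six toxicities that moment coincides with the start of a taper when steroids were given.

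The firm size is structural: no steroid limit in any of the seven restart cells, and no steroid limit in either column for Grade 2 hepatic events. The calendar result of one or two doses inside a minimum-length taper assumes dosing resumes at the next scheduled Day 1. It would be tempting to read those counts as patients put at risk or as doses the change would avoid; they are neither. The size of the benefit cannot be derived. The conclusion would weaken or fall away if the ECI guidance document sets a restart dose.

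**What to change.** First check the ECI guidance document for a restart condition. If it has none, amend Table 3 as follows.

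- In all seven rows with a Grade 0-1 restart condition, add: *and, if corticosteroids were given, the dose is down to 10 mg/day or less (prednisone equivalent)*. Include the row for all other toxicity: it already carries the 10 mg stop and so anticipates steroid use, and leaving it silent beside six explicit rows would suggest that any dose is acceptable there.
- In the Grade 2 hepatic row, add the 12-week steroid stop used in the other six. Without it, a patient whose liver tests had resolved but who could not taper would be barred from restarting with no matching stop.

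The cost is eight cell edits (seven restart cells and one discontinuation cell) by amendment. No new procedure is needed, because medication is already reviewed at each cycle. Some restarts will come later, and a few hepatic cases unable to taper would stop. A minimum-length taper still fits the 12-week limit, counted from the last dose before the hold, if it begins by day 56 (12 × 7 − 28 = 84 − 28 = 56).

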7. Be willing to provide fresh tissue for biomarker analysis, and, based on the adequacy of the tissue sample quality for assessment of biomarker status. Repeat samples may be required if adequate tissue is not provided. Newly obtained endoscopic biopsy specimens are preferred to archived samples and formalin-fixed, paraffin-embedded (FFPE) block specimens are preferred to slides.
 - a. *Newly-obtained is defined as a specimen obtained up to 6 weeks (42 days) prior to initiation of treatment on Day 1. Subjects for whom newly-obtained samples cannot be provided (e.g. inaccessible or subject safety concern) may submit an archived specimen.*
 - b. *Collection of an archived tissue sample will also be requested (where available) to support evaluation of the clinical utility of biomarker assessment*

in newly obtained vs. archived tissue samples; however, a subject will not be precluded from participating in the study if an archived tissue sample is not available for collection or is otherwise insufficient for analysis.

8. Have a performance status of 0 or 1 on the ECOG Performance Scale.
9. Demonstrate adequate organ function as defined in Table 1, all screening labs should be performed within 10 days of treatment initiation.

Table 1 Adequate Organ Function Laboratory Values

System	Laboratory Value
Hematological	
Absolute neutrophil count (ANC)	$\geq 1,500 / \text{mcL}$
Platelets	$\geq 100,000 / \text{mcL}$
Hemoglobin	$\geq 9 \text{ g/dL}$ or $\geq 5.6 \text{ mmol/L}$ without transfusion or EPO dependency (within 7 days of assessment)
Renal	
Serum creatinine OR Measured or calculated ^a creatinine clearance (GFR can also be used in place of creatinine or CrCl)	$\leq 1.5 \times$ upper limit of normal (ULN) OR $\geq 60 \text{ mL/min}$ for subject with creatinine levels $> 1.5 \times$ institutional ULN
Hepatic	
Serum total bilirubin	$\leq 1.5 \times$ ULN OR Direct bilirubin \leq ULN for subjects with total bilirubin levels $> 1.5 \text{ ULN}$
AST (SGOT) and ALT (SGPT)	$\leq 2.5 \times$ ULN OR $\leq 5 \times$ ULN for subjects with liver metastases
Albumin	$\geq 2.5 \text{ mg/dL}$
Coagulation	
International Normalized Ratio (INR) or Prothrombin Time (PT)	$\leq 1.5 \times$ ULN unless subject is receiving anticoagulant therapy as long as PT or PTT is within therapeutic range of intended use of anticoagulants

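### The hepatic row of Table 3 and its footnote 1 are not reconciled for liver-metastasis patients who enter with Grade 2 AST or ALT

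*Combined protocol and SAP*

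**What the plan says.** Table 1 in section 8.1.2 limits AST and ALT at entry to 2.5 × ULN in general and to 5 × "ULN for subjects with liver metastases".

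Table 3 in section 8.2.1.2 is titled "Dose Modification Guidelines for Drug-Related Adverse Events". Its row "AST, ALT, or Increased Bilirubin" has two lines:

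- **Grade 2.** Hold; restart when "Toxicity resolves to Grade 0-1"; discontinue if "Toxicity does not resolve within 12 weeks of last dose". Nothing in this line refers to a footnote.
- **Grade 3-4.** The cell on restart timing reads "Permanently discontinue (see exception below" and carries the mark of footnote 1. The neighbouring cell, in the column on discontinuing the subject, orders a permanent stop and carries no mark.

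Footnote 1 begins "For patients with liver metastasis who begin treatment with Grade 2 AST or ALT, if AST or ALT increases" and continues "by greater than or equal to 50% relative to baseline and lasts for at least 1 week then patients should be discontinued". It says nothing about a rise that is smaller or shorter than that.

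Two other places bear on the same question. The hepatic part of section 8.4.1 has Grade 2 events followed with more frequent liver tests until values are back at baseline. Exclusion criteria 6 and 7 in section 8.1.3 accept either Grade 1 or less, or the baseline level, as recovery from earlier treatment.

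**The concern.** The protocol knowingly admits patients who start at Grade 2, but the row is written as if everyone starts at Grade 0-1. Three difficulties follow for Grade 2 starters:

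1. A drug-related rise that meets the footnote's trigger without leaving Grade 2 is covered by two instructions that differ: hold with possible restart, or discontinue.
2. For a drug-related rise that reaches Grade 3 without meeting the trigger, one cell orders a permanent stop. The next points to an exception, but the text it points to is itself a stopping rule and gives no action below its threshold.
3. Once held at Grade 2, the patient can restart only at a value lower than the one at which the protocol found the patient eligible, and is discontinued if that is not reached in 12 weeks.

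The stake is first of all safety and consistent treatment. Section 10.1.3 requires laboratory results to be judged acceptable before each dose, so the question can recur at every cycle. Whatever is decided stays in the primary analysis, because section 11.1.1.1 counts every dosed patient in the ORR denominator and section 8.7 rules out replacement.

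**Working it through.** The plan gives no figure on this point, so there is none to reproduce. The check applies the row and the footnote to the same pairs of values.

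**Inputs from the documents.** Entry limit 5 × ULN with liver metastases (Table 1). Row actions by grade (Table 3). Footnote trigger: a value of at least 1.5 × baseline for at least 1 week.

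**Assumed inputs.** Section 18.2 adopts CTCAE version 4.0 without printing the AST/ALT cut-offs. The check takes Grade 2 as above 3.0 and up to 5 × ULN, then varies the lower bound from 2.5 to 3.0 and the Grade 2/3 boundary from 4.5 to 6. Every rise is taken as judged drug-related, and every rise of 50% or more as lasting at least 1 week.

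**Row and footnote side by side** (values in multiples of ULN):

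| Baseline | On treatment | Ratio | Hepatic row | Footnote 1 |
|---|---|---|---|---|
| 3.1 | 4.7 | 4.7/3.1 = 1.52 | hold, restart possible | discontinue |
| 4.5 | 5.5 | 5.5/4.5 = 1.22 | permanent stop (unmarked cell) | trigger not met, no action stated |
| 4.5 | 4.7 | 4.7/4.5 = 1.04 | hold | trigger not met, no action stated |
| 3.1 | 5.2 | 5.2/3.1 = 1.68 | permanent stop | discontinue |
| 5.0 | 7.5 | 7.5/5.0 = 1.50 | permanent stop | discontinue |

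The first line is a direct conflict that needs no inference. In the second and third lines the row gives an instruction and the footnote is silent. In the last two lines both texts end in discontinuation.

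**Which baselines are affected.** Let b be the baseline and U the Grade 2/3 boundary. The trigger 1.5b lies within Grade 2 when b ≤ U/1.5:

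- U = 5: 5/1.5 = 3.33
- U = 4.5: 4.5/1.5 = 3.0
- U = 6: 6/1.5 = 4.0

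At or below that point, the first difficulty covers values from 1.5b to U. Above it, the second covers values over U and under 1.5b; with U = 5 and b = 5 that is 5 to 1.5 × 5 = 7.5 × ULN. At one corner of the assumed range the first difficulty disappears: if Grade 2 starts above 3.0 and Grade 3 above 4.5, no Grade 2 starter has a baseline of 3.0 or less, and only the second remains.

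**Restart level.** With a baseline of 4.0 and Grade 1 ending at 3.0, restart needs 3.0/4.0 = 0.75 of baseline, a fall of 25%. If Grade 1 ends at 2.5, it needs 2.5/4.0 = 0.625, a fall of 37.5%. The size depends on the cut-offs. The direction does not, because Grade 0-1 lies below Grade 2 by construction.

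**The case against.** The best defence is that footnote 1 is labelled as an exception to the Grade 3-4 line, so a difference between the two is intended: a specific rule displaces a general one for a named group. That largely answers any charge that the two texts simply oppose each other at Grade 3-4. It does not supply the missing action below the trigger, explain the unmarked neighbouring cell, or reach the Grade 2 line, to which no exception is attached.

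A second defence is scope. Table 3 covers drug-related events only, and section 10.2 counts the worsening of an existing condition as an adverse event only if it is clinically significant. A reader might infer that a patient who enters at Grade 2 must be held at once, or after any small drift. The documents do not support that: an unchanged Grade 2 baseline does not by itself trigger the hold, and a small rise does so only if it is judged a drug-related event. By the same token, it cannot be said that treatment would end for reasons unrelated to tolerance.

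Third, the cut-offs come from outside the documents, and the affected range of baselines moves with them. That is correct, which is why a range is shown. The missing action below the trigger and the restart problem are visible in the text without any cut-off.

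**Conclusion.** The point stands as an unreconciled set of stopping and restart rules for one foreseen group: liver-metastasis patients who start at Grade 2. Under the assumed 5 × ULN boundary, a Grade 2 starter meets the hold-versus-discontinue conflict at baselines up to about 3.3 × ULN and the unfinished exception above that. The divide moves between 3.0 and 4.0 as the boundary moves from 4.5 to 6. The restart condition affects any of these patients once held for a drug-related Grade 2 event. It also sits uneasily with section 8.4.1 and with the two exclusion criteria, all of which recognise baseline.

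Two stronger readings are tempting and should not be drawn. One is that a single value can mean continue, hold or permanent stop. Continuing treatment is never written for these patients; it can only be read into the footnote's silence. For one patient at one value, at most two readings compete. Different outcomes for patients with different baselines are what a baseline-relative rule produces by design. The other is that the ambiguity biases ORR. The documents do not say how many of the approximately 40 patients will have liver metastases, start at Grade 2 and then have a drug-related rise, so no effect on the primary result can be shown.

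**What to change.** The sponsor and the investigator should reconcile the Grade 2 line, both Grade 3-4 cells, footnote 1 and the hepatic text of section 8.4.1 with the 5 × ULN entry limit. For Grade 2 starters, one instruction should then apply in each of three situations: a rise that meets the footnote's trigger within Grade 2, a rise that reaches Grade 3 without meeting it, and restart after a Grade 2 hold. The text should state which cells the footnote governs, what applies below its trigger, and whether the restart condition is meant to differ from the baseline wording used elsewhere. Which rule or threshold is right is a clinical decision, and no view on it is given here.

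The cost is one table row, one footnote and, if needed, a sentence in section 8.4.1. AST and ALT are already collected at screening and on study, so no new data are required. The sample size and the analysis do not change.
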